### **Longitudinal Model/Sensitivity Analysis**

To assess the longitudinal association between outcomes and time-varying treatment (*i.e.* patients switch treatment from Genotropin to Ngenla or vice versa at any time-point), a propensity model approach will be applied to calculate the inverse probability of treatment weights (IPTW). This model is assumed to control for time-varying confounding when time-varying treatments are used in longitudinal analyses.

The IPTW will be calculated using propensity score model in which the choice of the treatment at each visit will be considered as the outcome (Genotropin vs Ngenla) and the pre-specified baseline characteristics (See Table 9-3 Model Covariates) as independent variables. Once IPTWs per patient are derived, the models described in the Repeated Measure model will be applied with the weights. The models will include treatment group (time-varying covariate), time (in years) and IPTW. This approach will be considered as a sensitivity analysis *to assess the impact of treatment switching*.

Detailed methodology for summary and statistical analyses of data collected in this study will be documented in a statistical analysis plan (SAP), which will be dated, filed, and maintained by the sponsor. The SAP may modify the plans outlined in the protocol; any major modifications of primary endpoint definitions or their analyses would be reflected in a protocol amendment.

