#### Rationale and background

Human growth hormone (hGH) is a 191-amino-acid pituitary protein that stimulates production and release of insulin-like growth factor-I (IGF-I). Growth hormone (GH) and IGF-I are the primary mediators of the promotion of growth in children and play a role in the regulation of body composition and metabolism in children and adults. Growth hormone deficiency (GHD) results in inadequate levels of GH and IGF-I, which subsequently results in abnormal linear growth in children. Children with GHD have been treated with daily administration of recombinant hGH replacement therapy for many years which has been proven to be safe and effective.

Recombinant hGH has also been approved in many countries around the world for other conditions associated with growth failure and/or abnormal body composition. Children with GHD, Turner Syndrome (TS), Small for Gestational Age (SGA) and Idiopathic Short Stature (ISS) have been treated with daily administration of recombinant hGH replacement therapy for many years. Children with Prader-Willi syndrome (PWS) have also been treated with hGH for both the associated growth failure and abnormal body composition.

The burden of daily administration may cause sub-optimal adherence and limit the therapeutic utility of existing formulations of recombinant hGH. Ngenla (somatrogon) is a long-acting, once-weekly subcutaneously administered form of hGH, currently approved in many countries around the world for use as a long-term treatment in children with growth failure due to an inadequate secretion of endogenous GH.

PROGRES 2.0 is a multi-country, non-interventional, observational cohort study with the objective to assess the long-term effectiveness and safety of both Genotropin (somatropin) and Ngenla (somatrogon), at the discretion of the treating physician in routine clinical practice. This study will obtain real world data as a sub-study of the Global Registry for Novel Therapies in Rare Bone and Endocrine Conditions (GloBE-Reg). GloBE-Reg is an international registry project that obtains data on effectiveness and long-term safety through the collection of real-world data on all available forms of growth hormone and supports sub-studies focusing on various aspects of interest to treating

090177e1a57a0182\Approved\Approved On: 16-Feb-2026 13:43 (GMT)

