### 8.2. Setting

The source population for this study will be the subset of patients contributing data to the GloBE-Reg registry who are treated with either long acting Ngenla (somatrogon) or daily hGH Genotropin (somatropin) at the discretion of the prescribing physician. This population is thought to be a representative sample of children treated with Ngenla (somatrogon) and Genotropin (somatropin) across the world. Data will be included from eligible participants of any age who meet the study criteria and who receive care at centers enrolled in GloBE-Reg that have agreed to share their data with Pfizer during the data collection period. The registry is growing and additional centers around the world are expected to be included over the course of the study period.

The data collection period is from September 30, 2025 to August 31, 2035. No sampling will be performed. Participants can be located anywhere in the world and will be followed up to 10 years until the end of the study or one of the following occurs: withdrawal of consent, discontinuation of

either Ngenla (somatrogon) or Genotropin (somatropin), discontinuation from the GloBE-Reg registry, lost to follow up or death.

The treating physician will follow patients treated with Genotropin (somatropin) or Ngenla (somatrogon) as per routine clinical practice and will collect and enter relevant patient data as part of the defined minimum data set collected by the GloBE-Reg registry.

During the study, duration of treatment exposed will be defined as:

Genotropin/Ngenla: (last dose date – baseline date + 1)/365.25,

where baseline date is the initial visit date on the Reported Outcomes eCRF form.

The data collected via GloBE-Reg will be de-identified and sent to Pfizer for analysis. Pfizer will analyze the data to evaluate treatment effectiveness, safety, adherence and compliance.

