Exposure scenarios: Medication error	outcome	GloBE-Reg database	Categorical  - Visit date - Date of assessment - Type of medication error (accidental/intentional) - Classification (wrong drug/route/frequency/dose/other) - Date when it occurred - Date when it was reported to physician - Report to authorities details - Adverse events associated with medication error - Other details  See SAP
---	---------	--------------------	---

Baseline date is the initial visit date on the Reported Outcomes eCRF form.

The potential covariates and confounders that will be considered for the models in addition to treatment (Genotropin and Ngenla) are the following baseline variables, classified into different categories:

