**Repeated Measures**

This model will only be performed with those patients without treatment switch until a given time point. Continuous variables will be analyzed by a Mixed Model for Repeated Measures (MMRM) under the MAR framework, including all post baseline timepoints data as outcome variables and baseline data as a covariate including the relevant patient/disease characteristics. Repeated time variable will be modeled as a continuous variable and treatment (Genotropin versus Ngenla) as a class variable with an unstructured covariance and least square means along with 95% CI will be presented.

The adjusted mean changes from Baseline at Month 6, 12, 18, 24, etc., for each treatment group will be estimated in the framework of this model, as well as the between group differences and the 95% CIs for the adjusted mean, when applicable.

The MMRM model will be implemented using SAS® (version 9.4 or higher) generalized linear mixed procedure (PROC MIXED) with an unstructured correlation matrix to model the within-patient errors. If this model does not converge, a heterogeneous Toeplitz covariance structure followed by the

090177e1a57a0182\Approved\Approved On: 16-Feb-2026 13:43 (GMT)

heterogeneous first-order autoregressive covariance structure will be considered. Parameters will be estimated using the Newton-Raphson algorithm. Denominator degrees of freedom will be estimated using the Kenward-Roger approximation.

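### Baseline is the first registry visit, not study-drug start, so growth before Ngenla or Genotropin can count in that drug's change from baseline, and the undefined 'switch' may not remove it

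*Protocol*

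**What the plan says.** Section 8.3 fixes time zero: "Baseline date is the initial visit date on the Reported Outcomes eCRF form". Section 8.2 repeats this and computes treatment exposure in years from the same date, with the formula ending "last dose date – baseline date + 1)/365.25".

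The primary model (section 8.7, Repeated Measures) is an MMRM "including all post baseline timepoints data as outcome variables and baseline data as a covariate", with "treatment (Genotropin versus Ngenla) as a class variable". Its population is restricted: "This model will only be performed with those patients without treatment switch until a given time point". That paragraph does not say what a switch is.

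The only description of switching is in section 8.7, Longitudinal Model/Sensitivity Analysis. There it explains time-varying treatment for the weighted analysis: "patients switch treatment from Genotropin to Ngenla or vice versa at any time-point". In the propensity model, "the choice of the treatment at each visit will be considered as the outcome (Genotropin vs Ngenla").

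On who can enter, the Abstract (Rationale and background) describes the registry as the "collection of real-world data on all available forms of growth hormone". Section 8.2.1 asks that the participant be receiving one of the two drugs, without tying this to the baseline visit. Section 8.7 states that everything received from the registry is analysed.

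**The concern.** The primary objective is a comparison of two named products. It needs a time zero at which each participant is on, or is starting, the product to which later change is credited. The protocol's time zero is an administrative date in a registry of all GH products.

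A child may have a first Reported Outcomes visit on another GH brand, or on none if such visits exist, and start Ngenla some months later. That child becomes eligible, keeps the early visit as baseline and contributes to the Ngenla mean. The month-12 change then mixes growth before and on Ngenla. The same can happen to a Genotropin participant.

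If this happened more often in one arm, the between-drug contrast would be biased. If it were balanced, both arms' descriptive means would still misstate growth on the drug.

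**Working it through.** The protocol states no figure to reproduce. The check is to follow one participant through the rules and then size the error.

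**Following the rules.** Take a child whose first Reported Outcomes visit is at month 0 and who starts Ngenla at month g.

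1. *Eligible?* Yes, once on Ngenla. Section 8.2.1 does not require use at month 0, and data arrive every 6 months (section 8.6), so a child can qualify after earlier visits.
2. *Baseline?* Month 0 (sections 8.2 and 8.3).
3. *Visits before g removed?* No rule does so. The stop rules in section 8.2 end follow-up when the study drug is discontinued. They cover later moves away from it, not time before it.
4. *Out of the MMRM as a switcher?* This depends on the reading:
   - If a switch is any product change, a child coming from another brand leaves.
   - If a switch is only Genotropin to Ngenla or the reverse, that child stays.
   - A child coming from no treatment stays on both readings, because starting therapy is not switching.
5. *Adjusted away?* No. Table 8-3 lists naive status and time since first rhGH. These describe GH history at baseline, not how much of the outcome window was on the study drug. A child untreated at month 0 who starts at month 6 and one who starts on day 0 are both naive.
6. *Weighted analysis?* A visit before g fits neither level of the two-level propensity outcome. Even if it dropped out for that reason, change from baseline at later visits would still run from month 0.

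**Size per affected child.** Inputs from section 6 are 10.10 cm/year on Ngenla and 9.78 cm/year on daily hGH, a difference of 10.10 − 9.78 = 0.32. Assumptions not in the protocol are a gap of g months, an untreated velocity v0 of 4 to 5 cm/year, and first-year growth measured from baseline. The share of the 12-month window off the drug is g/12, so

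shortfall = (g/12) × (10.10 − v0).

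| g (months) | Share of year off drug | Shortfall, v0 = 5 | Shortfall, v0 = 4 | Share of one arm that shifts its mean by 0.32 |
|---|---|---|---|---|
| 3 | 25% | 0.25 × 5.10 = 1.275 cm | 0.25 × 6.10 = 1.525 cm | 0.32/1.275 = 25% to 0.32/1.525 = 21% |
| 6 | 50% | 0.50 × 5.10 = 2.55 cm | 0.50 × 6.10 = 3.05 cm | 0.32/2.55 = 13% to 0.32/3.05 = 10% |
| 9 | 75% | 0.75 × 5.10 = 3.825 cm | 0.75 × 6.10 = 4.575 cm | 0.32/3.825 = 8% to 0.32/4.575 = 7% |

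The last column assumes that nobody in the other arm is affected.

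**From another GH brand.** Assume the other brand grows at the daily rate of 9.78. For g = 6, first-year growth is 0.5 × 9.78 + 0.5 × 10.10 = 9.94, a shift of 0.16 cm. With 10% of an arm affected, its mean moves by 0.10 × 0.16 = 0.016 cm. With everyone affected it moves by 0.16 cm, half the pivotal-trial difference.

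The share g/12 is time off the drug, not bias. The bias is that share multiplied by the difference in growth rates.

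**The case against.** A reader might infer that the protocol defines a switch as a Genotropin–Ngenla change only, so the primary MMRM certainly keeps children who come from another brand. The text does not go that far. The description is a gloss on time-varying treatment in the sensitivity analysis, and nothing carries it into the Repeated Measures paragraph as an exhaustive definition. In ordinary usage a move from another brand is a switch. What stands is that the primary population has two readings.

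A reader might also infer that the comparison is biased against Ngenla, because a newer weekly product would more often follow something else. No section supports this. Where the something else is Genotropin, it is already a switch. The protocol's counts (365 Genotropin and 157 Ngenla participants in June 2025, over 3500 in the registry) do not show how many had earlier visits off the study drug.

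The inclusion criterion is in the present tense, and the exposure formula makes sense only if the child is on the drug at baseline. That suggests what the authors had in mind, but it is not a rule. No section documents untreated children with Reported Outcomes visits, so that case is possible rather than shown.

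Section 8.3 leaves operational definitions to the SAP. That would answer a missing detail. Here the protocol itself states the baseline rule, twice, and section 8.7 requires a protocol amendment for major changes to primary endpoint definitions or analyses.

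Naive status is a covariate and a prespecified subgroup for the height outcomes. This separates previously treated children in reporting but does not move time zero.

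**Conclusion.** The point holds as a defect in the baseline rule, made worse by an undefined switch. As written, growth before the study drug can enter that drug's change from baseline, and no covariate, stop rule or weighting removes it.

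The size depends on the source of the gap. For an untreated gap the error per child could be large: about 2.5 to 3 cm of first-year height for 6 months, assuming 4 to 5 cm/year untreated. On those assumptions, 10% to 13% of one arm alone would shift its mean by 0.32 cm. For a gap on another GH brand the error is likely small, about 0.16 cm per child for 6 months if that brand grows at the pivotal-trial daily rate.

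How often either occurs, and whether it differs between arms, cannot be learned from the protocol. The documents therefore show a rule that permits bias, not a bias of known direction. The illustration covers height only. Errors in BMI, bone age and IGF-I were not sized.

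**What to change.** For the effectiveness endpoints:

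- **Index date (sections 8.2 and 8.3).** Use the later of the first registry visit and the start of the current Genotropin or Ngenla course. Take as baseline the nearest measurement on or before that date.
- **Switch (section 8.7, Repeated Measures).** State that a switch is any change of GH product after the index date.
- **Analysis data.** Exclude visits before the study drug, or on other products, from both the MMRM and the IPTW data.

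Redefining the switch alone is not enough, because it leaves the start from no treatment untouched. The index date does the main work.

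The cost is wording and programming. The start date of current therapy and the commercial drug name are already among the section 8.3 variables. The downside is that participants with no measurement near the start of the study drug lose a usable baseline. Their number should be reported by arm.

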**Table 8-3 Model Covariates**

Priority Order*	Model Covariates	Propensity Score Model Covariates - Categories
7	Geographic region	Region (Europe, NA, Japan and RoW)
1	Demographics	Age (in years), Sex
2	Clinical characteristics	Height, Weight
3	Naive to GH status	Naïve to GH/Non-Naïve to GH
4	Peak GH levels	≤3 ng/mL, >3 ng/mL to ≤7 ng/mL, >7 ng/mL to 10 ng/mL, >10 ng/mL
5	Duration of GH (time from first rhGH therapy)	
6	Time since start of the study (in months)	

090177e1a57a0182\Approved\Approved On: 16-Feb-2026 13:43 (GMT)

\*This priority order will be used to remove the least priority variables in case of non-convergence issues for the model. Additional variables and its priority order can be decided during the analysis. Relevant patient/disease characteristics, including baseline value of the variable to be analyzed, will also be included whenever applicable.

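### The switching analysis is said to control time-varying confounding, but its weights use baseline covariates only, so confounding of switching by on-treatment response is not controlled

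*Protocol*

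**What the plan says.** Section 8.7, Longitudinal Model/Sensitivity Analysis, plans inverse probability of treatment weighting for patients who move between Genotropin and Ngenla. It says of this approach: "This model is assumed to control for time-varying confounding when time-varying treatments are used in longitudinal analyses".

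The next paragraph sets out the weight model. Its outcome is the product used at each visit. Its predictors are "pre-specified baseline characteristics (See Table 9-3 Model Covariates) as independent variables". There is no Table 9-3; the list is Table 8-3, Model Covariates. Section 8.3 introduces that list by saying that the candidate covariates "are the following baseline variables, classified into different categories". The entries are region, age, sex, height, weight, GH-naive status, peak GH, duration of GH therapy and time since study start. The footnote adds: "Relevant patient/disease characteristics, including baseline value of the variable to be analyzed, will also be included whenever applicable". It also lets further variables be chosen during the analysis, but names none.

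The weights are described as derived per patient, and the Repeated Measures models are then refitted with them: "The models will include treatment group (time-varying covariate), time (in years) and IPTW". The Repeated Measures section specifies an unstructured covariance and says: "Denominator degrees of freedom will be estimated using the Kenward-Roger approximation". It limits the main MMRM to patients who have not switched by the time point concerned.

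Table 8-7, Overview of Effectiveness Analysis, lists MMRM + IPTW as Statistical Method 2 in all eight rows, every one of them a primary outcome.

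**The concern.** Time-varying confounding arises when something that changes after baseline affects both the next treatment choice and the later outcome. Here that could be recent growth, IGF-I, missed doses, pubertal progress or an adverse event. None of these is in the weight model, and neither is the product the patient was on before. The sentence therefore claims a property that the model specified directly after it does not have.

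The protocol makes the threat plausible. In the Section 8.3 variable table, poor efficacy and adverse events are among the recorded reasons for stopping therapy, and growth and IGF-I are among the reasons for changing dose. If poorly growing children tend to change product, part of their poor growth is credited to the product they move to. A reader of the report would be told that this had been dealt with.

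**Working it through.** The protocol states no figure to reproduce: no switching rate, effect size or SD. The check is a short argument from the text, then a simulation whose settings are all assumptions apart from the expected study size.

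**Step 1: what the weights balance.** Let B be the baseline covariates, A(t) the product at visit t, and H(t) the post-baseline history (prior treatment, growth, IGF-I, adherence, puberty, adverse events). The specified weight for a patient on product a is

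w = 1 / P(A(t) = a | B).

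Among patients with given B and H(t), the expected weight falling on product a is

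P(A(t) = a | B, H(t)) / P(A(t) = a | B).

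This equals 1 for every H(t) only if, given B, treatment choice does not depend on H(t), that is, only if there is no time-varying confounding to control. Otherwise the weighted groups are balanced on B and unbalanced on H(t). Duration of GH therapy and time since study start could be updated at each visit, but they are clocks and carry no information on response.

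**Step 2: size, under assumptions.** Settings: 2,000 + 700 = 2,700 patients (Section 8.5), about 26% starting on Ngenla (700/2,700 = 0.259), 6 visits, true effect 0, outcome SD about 1, 20 replicates per setting. Switching to Ngenla becomes more likely as the driver worsens, with log-odds slopes of 0.5, 1.0 and 1.5 per SD; 20-29% of patients ever switch. Weights enter by rescaling the residual covariance for each patient-visit. The entries below are bias in SD units at the three slopes.

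| Driver of switching | Unweighted, unstructured | Baseline-only weights, unstructured (as planned) | Baseline-only weights, independence | Time-updated weights, independence |
|---|---|---|---|---|
| Previous value of the outcome | -0.002 / -0.002 / -0.003 | -0.037 / -0.063 / -0.075 | -0.085 / -0.178 / -0.271 | -0.004 / -0.005 / -0.010 |
| Another time-varying factor | -0.057 / -0.113 / -0.169 | -0.077 / -0.144 / -0.201 | -0.070 / -0.144 / -0.216 | -0.003 / -0.001 / -0.010 |

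Monte Carlo standard errors are 0.004 to 0.010. The time-updated weights are stabilised, cumulated over visits, and use prior treatment, the previous outcome and the other factor.

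The planned analysis is thus biased by -0.037 to -0.201 SD. In these settings the baseline-only weights moved the unstructured model further from zero than no weighting did.

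**Step 3: what the baseline weights do achieve.** A second simulation used working independence.
- With no time-varying driver and response correlated 0.6 with baseline, the bias was 0.094 SD unweighted and 0.005 with baseline-only weights. Baseline confounding is removed.
- With response-driven switching at slope 1.0 and response unrelated to baseline, it was -0.174 unweighted and -0.170 weighted. Almost nothing is removed.
- At the same slope with response correlated 0.6 with baseline, the baseline-only result was -0.103.
- Time-updated weights gave +0.002 to +0.011 in every setting of this simulation.

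**The case against.** **The planned model may absorb part of the bias.** This stands. When the previous value of the same outcome drives switching, the unstructured covariance reduces the bias of the baseline-weighted fit by 56% to 72% relative to independence (1 - 0.037/0.085 = 0.56; 1 - 0.075/0.271 = 0.72). Baseline predictors of response also help: -0.103 against -0.170. A reader might infer that switching stays fully confounded; the evidence does not support that. However, when another factor such as IGF-I or adherence is the driver, the unstructured model removes almost nothing.

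**Switching is handled elsewhere.** Partly so. The main MMRM deals with it by restriction to patients who have not switched, so it would be wrong to infer that the weighted model is the protocol's only handling of switching, or that this error reaches Statistical Method 1. It is, though, the only prespecified analysis that uses data after a switch. Section 8.2 ends follow-up at discontinuation of either product, which read literally would limit post-switch data. Since an analysis of switchers is planned, I assume some will exist.

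**The covariate list is open and the SAP holds the detail.** The Table 8-3 footnote does allow more variables, but names no time-varying one, and a choice made during analysis cannot support a prespecified claim. The protocol itself fixes the predictors as baseline and makes the claim, so this is not an item left to the SAP. Truncation and weight diagnostics are properly SAP matters.

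**IPTW as a covariate, and the standard errors.** Listing IPTW among the contents of the model could be read as making it a covariate. It follows directly on a statement that the models are applied with the weights, so loose wording is likelier. Kenward-Roger is stated for the unweighted MMRM; its use in the weighted fit is an inference from the reuse of that model. Both need only clearer wording.

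**Response-driven switching is assumed, and the limitations are acknowledged.** True: the registry fields give reasons for stopping and for changing dose, not for changing product. Section 8.9 also concedes that confounding cannot be excluded. Neither makes the sentence correct.

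**Conclusion.** The concern holds. The specified weights can correct baseline confounding only, so the stated control of time-varying confounding does not follow from the model. Confounding of switching by on-treatment response is left to whatever the baseline covariates and the covariance structure happen to absorb.

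That conclusion rests on the protocol text alone. The size does not: about -0.04 to -0.20 SD under the planned covariance is illustrative and depends on the assumed switching rates, drivers and slopes. The near-zero comparison was run under working independence, not with the unstructured covariance.

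It is tempting to set the bias beside the pivotal-trial difference in height velocity, 10.10 - 9.78 = 0.32 cm/year. The protocol gives no SD for height velocity, so no figure in cm/year is claimed.

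The label of sensitivity analysis and the descriptive aim limit the consequence but do not remove it. Method 2 is reported for every primary outcome, and a check that is wrongly described as controlling this bias gives false reassurance.

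**What to change.** Preferred change, in the protocol and carried into the SAP:
- Model treatment at each visit on prior treatment, the baseline covariates, and the last recorded height SDS or height velocity, IGF-I SDS, missed doses, pubertal stage and adverse events.
- Use stabilised weights, cumulated over visits and defined per patient-visit rather than per patient.
- State a robust or bootstrap variance for the weighted fit in place of Kenward-Roger, and state its working covariance. Independence is the structure under which the time-updated weights were checked.
- Describe IPTW as a weight, not as something the model includes.
- Correct the reference from Table 9-3 to Table 8-3.

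Minimum change: if the baseline-only weights are kept, delete the sentence on time-varying confounding and state that only baseline confounding is addressed.

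Cost: the minimum change is a matter of wording. The preferred one needs programming but no new data collection, since the registry has fields for all these items. It brings somewhat wider intervals. Lagged values will also be missing, because assessments follow routine practice and several fields can be recorded as unknown or not performed. Section 8.7 allows no imputation, so a rule for missing lagged values must be written down; without one, patient-visits would drop out of the weighted analysis.

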**Table 8-7 Overview of Effectiveness Analysis**

Outcome	Primary/Secondary	Statistical Method 1	Statistical Method 2	Statistical Method 3
Annual HV	Primary	MMRM, 95% CI	MMRM + IPTW, 95% CI	Descriptive stats
Height standard deviation score (SDS) and change in height SDS	Primary	MMRM, 95% CI	MMRM + IPTW, 95% CI	Descriptive stats
HVSDS	Primary	MMRM, 95% CI	MMRM + IPTW, 95% CI	Descriptive stats
Change in annual BMI	Primary	MMRM, 95% CI	MMRM + IPTW, 95% CI	Descriptive stats
Change in annual BMI SDS	Primary	MMRM, 95% CI	MMRM + IPTW, 95% CI	Descriptive stats
Change in Bone age	Primary	MMRM, 95% CI	MMRM + IPTW, 95% CI	Descriptive stats
Change in IGF	Primary	MMRM, 95% CI	MMRM + IPTW, 95% CI	Descriptive stats
Change in IGF-I SDS	Primary	MMRM, 95% CI	MMRM + IPTW, 95% CI	Descriptive stats

090177e1a57a0182\Approved\Approved On: 16-Feb-2026 13:43 (GMT)

[1] Continuous variables will be summarized using descriptive statistics which will include the number of patients with data to be summarized (n), mean, standard deviation (SD), median, first and third quartiles (Q1, Q3), minimum, maximum, and the number of missing observations. Descriptive statistics for categorical/qualitative variables will be presented with number of patients (count) and percentage and this will be presented in the format 'n (%)'.

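### Model-based Kenward-Roger inference is carried into the IPTW-weighted models, so nominal coverage of their 95% intervals is not assured

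*Protocol*

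**What the plan says.** Section 8.7, Repeated Measures, specifies the unweighted model: "PROC MIXED) with an unstructured correlation matrix to model the within-patient errors", followed by "Denominator degrees of freedom will be estimated using the Kenward-Roger approximation". Its right-hand side contains "baseline data as a covariate including the relevant patient/disease characteristics".

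Section 8.7, Longitudinal Model/Sensitivity Analysis, builds the weighted analysis by cross-reference: "the models described in the Repeated Measure model will be applied with the weights". The next sentence describes the contents more narrowly: "The models will include treatment group (time-varying covariate), time (in years) and IPTW". The section gives the role of the analysis: "This approach will be considered as a sensitivity analysis", aimed at the effect of treatment switching.

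Table 8-7, Overview of Effectiveness Analysis, lists "MMRM + IPTW, 95% CI" as Statistical Method 2 in all eight rows, each labelled primary. The protocol names no sandwich or bootstrap variance for the weighted model and does not say whether the weights are stabilised. It defers detailed methodology to the SAP.

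**The concern.** Kenward-Roger adjusts a model-based covariance matrix, so it takes the fitted likelihood as correct. When weights enter a likelihood of this kind, a patient with weight 4 is treated as measured with a quarter of the residual variance. A propensity weight means something else: that patient stands in for others who were less likely to receive the same drug. Two sources of error then go unaccounted for: the variance added by unequal weights, and the effect on the variance of having estimated the weights from the same data.

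At stake is how the sensitivity analysis is read. It is the modelled comparison built to use time-varying treatment, whereas the unweighted MMRM is limited to patients without a switch up to the time point. If its intervals are miscalibrated, agreement or disagreement between the two analyses cannot be judged from them.

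**Working it through.** The protocol gives no standard error, interval width or coverage for this analysis, so there is no figure to reproduce. Two checks were made.

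**Closed form.** Inputs from section 8.5: n0 = 2000 Genotropin, n1 = 700 Ngenla, N = 2700. Assumptions: one weight per patient, the same within-arm coefficient of variation (CV) of the weights in both arms, weights unrelated to the residuals, residual variance set to 1.

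- True variance of the treatment difference: (1/n0 + 1/n1)(1 + CV²), with 1/2000 + 1/700 = 0.001929.
- Model-based variance, stabilised weights (summing to n0 and n1): 1/n0 + 1/n1 = 0.001929.
- Model-based variance, unstabilised weights (summing to about N in each arm): 4/N = 4/2700 = 0.001481.
- SE ratio = √(model-based variance / true variance); coverage = 2Φ(1.96 × ratio) − 1.

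For example, unstabilised at CV 0.5: √(0.001481 / (0.001929 × 1.25)) = 0.784, coverage 87.6%.

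| CV | Unstabilised: ratio, coverage | Stabilised: ratio, coverage |
|---|---|---|
| 0 | 0.876, 91.4% | 1.000, 95.0% |
| 0.5 | 0.784, 87.6% | 0.894, 92.0% |
| 1.0 | 0.620, 77.6% | 0.707, 83.4% |

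By construction this formula cannot show intervals that are too wide, because it ignores estimation of the weights.

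**Simulation of the weighted MMRM.** Four visits, unstructured covariance, logistic propensity score estimated in each replicate, one weight per patient, no true treatment effect. N = 522 (365 + 157, the registry count at 30 June 2025) with 600 replicates, and N = 2700 with 300. Normal limits were used, since the degrees-of-freedom correction is negligible at these sizes. Cells show model-based SE divided by the empirical SD, then coverage, at N = 522.

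| Outcome model | Weights | CV about 0.25 | CV about 0.48 | CV about 0.85 |
|---|---|---|---|---|
| Covariates adjusted | Unstabilised | 0.85, 90.0% | 0.79, 88.7% | 0.68, 81.7% |
| Covariates adjusted | Stabilised | 1.01, 95.0% | 0.90, 93.5% | 0.79, 86.5% |
| Treatment and time only, moderate prognosis | Unstabilised | 1.04, 96.0% | 0.96, 93.0% | 0.73, 84.0% |
| Treatment and time only, moderate prognosis | Stabilised | 1.19, 98.0% | 1.10, 97.5% | 0.88, 91.2% |
| Treatment and time only, strong prognosis | Unstabilised | 1.53, 99.8% | 1.22, 98.7% | 0.80, 89.5% |
| Treatment and time only, strong prognosis | Stabilised | 1.79, 99.5% | 1.34, 98.0% | 0.93, 93.2% |

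CV is that of the treated-arm weights; in the last column it ran from 0.83 to 0.86. At N = 2700 (CV about 0.23 and 0.47) the ratio was 0.80 to 0.95 with adjustment and 1.23 to 1.72 with treatment and time only under strong prognosis. A larger registry therefore does not remove the problem.

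**Patient-clustered sandwich, same estimates.** With covariates adjusted, coverage was 91.8% to 95.7% at N = 522 and 93.7% to 95.7% at N = 2700. With prognostic covariates left out of the outcome model, the sandwich that takes the weights as known was mostly conservative: ratio 1.06 to 1.87, coverage 95.7% to 100%.

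**The case against.** The strongest reply is that the Kenward-Roger sentence belongs to the unweighted model, that the IPTW text names no variance estimator and no mechanism by which the weights enter, and that the SAP may settle both. Stabilisation and truncation are indeed ordinary SAP detail, and their absence alone would be no finding. But the protocol does more than stay silent. It applies the already specified models with weights, and those models come with a stated procedure and stated inference. Followed as written, the weighted intervals are model-based.

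A second reply is that little turns on it: this is a sensitivity analysis in a study without a priori hypothesis testing. That stands, and it limits the weight of the point.

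A reader might go further and infer that the weighted intervals are too narrow for every primary outcome. The documents do not support that. The section reuses a covariate-adjusted model but then lists only treatment, time and IPTW as contents. Under the second reading, with prognostic covariates in the propensity score, the model-based SE is often too large. Nor is this clearly the only analysis that keeps switchers: the unweighted MMRM can be read as using their data up to the switch, and the descriptive statistics state no exclusion.

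**Conclusion.** The point holds as one of calibration, without a fixed direction. The protocol carries a model-based variance with Kenward-Roger degrees of freedom into the weighted models, so nominal 95% coverage is not assured in any of the eight primary rows. The intervals can be too narrow (about 82% to 90% coverage with unstabilised weights and covariate adjustment), about right (stabilised weights of low spread with adjustment), or too wide (SE up to about 1.8 times what is needed, with treatment and time only and strongly prognostic propensity covariates).

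These sizes rest on assumptions that are not in the documents: the weight spread, the covariate effects, four visits, complete data, no switching and one weight per patient. Visit-specific weights with switching, the setting the section is meant for, were not simulated. The unweighted MMRM is unaffected. The correction is worth making because it is cheap, but it does not threaten the main analysis.

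**What to change.** In section 8.7, Longitudinal Model/Sensitivity Analysis, and in the SAP:

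- State that the IPTW models use stabilised weights.
- Replace the model-based Kenward-Roger inference for these models with a patient-level bootstrap that re-estimates the propensity model in each resample. A patient-clustered empirical (sandwich) variance is an acceptable alternative when the prognostic covariates are also in the outcome model. Where they are not, the bootstrap is preferable, because the simple sandwich was conservative there. The bootstrap itself was not simulated here.
- State whether the weighted outcome model keeps the baseline covariates of the unweighted MMRM, since this decides which variance is suitable.
- State that Kenward-Roger applies only to the unweighted MMRM.

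Clustering should be by patient; clustering by centre gives a different variance and is not interchangeable. Truncation of weights is a choice between bias and variance and may be left to the SAP. The cost is some wording and extra programming. Intervals may become wider or narrower than under the present text.
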